4.7.1.1 Overall exposure

The actual dose administered at each visit is calculated as:

(Total volume administered/Total volume prepared) * assigned dose.

The total BIVV009 dose is the summation of all actual doses administered in Part A.

The number of subjects with missing infusion due to COVID-19 will be presented.

4.7.2 Adverse events

General common rules for adverse events

AEs will be classified using the MedDRA system organ classes and preferred terms. MedDRA version 20.1 or higher will be used throughout the study.

In general, AEs will be analyzed based on *incidence*, defined as the proportion of subjects who had at least one occurrence of an event out of the number of subjects in the Safety Analysis Set. An adverse event listing will be provided and will include all adverse events reported with the onset and resolution study days relative to Day 0 (Study Day 1).

All summary table analyses will only include treatment-emergent adverse events unless noted otherwise.

Unless specified otherwise, system organ classes (SOCs) and preferred terms (PTs) within each SOC will be presented alphabetically. For the purpose of summarization, a subject is counted once in a SOC or preferred term if the subject reported one or more events in that SOC or preferred term. Unless specified otherwise, percentages will be based on the number of subjects in the Safety Analysis Set.

Overall Summary of Adverse Events

An overall summary of TEAEs will be provided which tabulates the number and percentage of subjects who experienced a TEAE, related TEAE, TEAE grade 3 or higher, TEAE infection of grade 3 or higher, TEAE thromboembolic event, TEAE within 24 hours of the start of infusion, TESAE, related TESAE, and TESAE infection; the number and percentage of subjects who discontinued treatment and/or the study due to a TEAE and the number and percentage of subjects who died on-study.

Treatment-emergent Adverse Events

The incidence of TEAEs will be summarized by SOC and preferred term.

Adverse Events in Descending Order of Incidence

A table will be provided which displays TEAE preferred terms in descending order of incidence. Only preferred terms will be included in this table (ie, the display will not include SOCs).

A similar table will be provided for Grade 3 or higher TEAEs. AEs for which the assessment of severity is missing will be included in this table in the TEAE Grade 3 or higher category.

Severity of Adverse Events

AEs are classified by the Investigator for CTCAE grades v4.03. A summary of TEAEs by system organ class, preferred term, and CTCAE grade will be presented. AEs with missing severity will be excluded from this table and listed separately to supplement the summary table. A subject will be counted once for each SOC and preferred term based on the greatest severity within that SOC and preferred term, respectively.

Relationship of Adverse Events to Study Drug

AEs are classified by the Investigator for relationship to study drug (“Not related,” “Possible,” and “Probable”). For summary tables, an AE with relationship of “Possible” or “Probable” will be considered “Related.” A summary of TEAEs by SOC, preferred term, and relationship (“Related” or “Not related”) will be presented. AEs with a missing relationship will be counted as “Related” in the summary table. A subject will be counted once for each SOC and preferred term based on the highest relationship within that SOC and preferred term, respectively.

Serious Adverse Events

Any AE reported as resulting in death, immediate risk of death (life threatening), inpatient hospitalization or prolongation of existing hospitalization, persistent or significant disability/incapacity, or a congenital/anomaly/birth defect will be classified as an SAE by the Investigator. An SAE may also be any other medically important event that, in the opinion of the Investigator, may jeopardize the subject or may require intervention to prevent one of the other outcomes listed above.

Treatment-emergent SAEs and treatment-emergent related SAEs will be summarized by system organ class and preferred term. Treatment-emergent SAEs will also be summarized by preferred term in descending order of incidence.

Adverse Events Leading to Treatment Discontinuation and/or Study Withdrawal

AEs leading to treatment discontinuation and/or study withdrawal will be listed. All AEs reported on the AE log for the item “Action Taken with Study Drug” with a response of “Study drug permanently discontinued” or for the item “Was the subject terminated from this study due to this AE?” with a response of “Yes” will be included.

Deaths on Study

A listing of deaths occurring on study will be provided.

Analysis of adverse events of special interest (AESIs)

AEs within 24 Hours after the Start of Infusion

All AEs within 24 hours after the start of infusion are captured in the eCRF. Incidence of AEs within 24 hours after the start of infusion will be summarized by SOC and preferred term.

Infections and Infections of \geq Grade 3 Severity

Infections will be captured based on MedDRA SOC of “infections and infestations.” Incidence of all infections of Grade 3 or higher will be summarized by preferred term.

Hemolytic Breakthrough

Proportion of subjects with hemolytic breakthrough (defined in [Section 4.1](#)) at any visit will be summarized. The date (visit) of onset and hemolytic lab parameters (ie, Hgb, bilirubin, LDH, and haptoglobin) over time will be listed for subjects with haemolytic breakthrough.

Anti-drug Antibody

Subjects who discontinue treatment early in Part A will be evaluated for anti-drug antibodies. Subjects with a positive anti-drug antibody will be listed along with the associated titer, if available.

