### 4.3.8 Immunogenicity endpoints

During Part A, ADA samples will be collected at predose on Day 0, 7, 35, 77, 133, 175 and on Day 182 (EOT) or at ET if a patient withdraws early. During Part B, ADA samples will continue to be collected at predose, on Days 189, 217, and 245, then routinely at 3-month intervals starting at Day 273 through the remainder of the study and at Safety Follow up visit 9 weeks after last dose. Samples will also be collected if a patient experiences a hematologic breakthrough or withdraws from the study.

In patients enrolled prior protocol v6.0 and having consented to the use of their blood samples for future research, ADA may be tested using available predose PD back-up samples.

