## 7.8.2 Methods of analysis

Adverse events will be classified using the Medical Dictionary for Regulatory Activities (MedDRA) System Organ Class and Preferred Term. Tabulations of TEAEs and serious TEAEs by frequency, relatedness, and severity will be presented. Patient listings will be provided for SAEs, AEs resulting in discontinuation of the study or study treatment, and all deaths. In addition, specific summary tables will be presented for hemolytic breakthrough, infections (Grade 3 or above), and thrombolytic events.

Changes from baseline in clinical laboratory parameters (except those considered efficacy and PD endpoints), vital signs, and ECG parameters will be summarized over time using descriptive statistics. The number and percentage of patients who have positive ADAs will be presented.

Concomitant medications and physical exam data will be displayed in listings only.

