1 INTRODUCTION

1.1 STUDY DESIGN

BIVV009-04 is a Phase 3, randomized, double-blinded, placebo-controlled, multicenter study in patients with primary cold agglutinin disease (CAD) without a recent history of blood transfusion. Eligible patients received study drug (BIVV009 or placebo) and underwent safety and efficacy assessments for 6 months (26 weeks) in Part A of the study.

Following completion of the initial 6-month treatment period, patients will roll into the long-term safety study (Part B) where they will continue to receive the study drug, BIVV009. After completion of all Part A EOT assessments, patients who qualify to roll-over into Part B will receive a cross-over loading dose, in a blinded manner, at the Week 26 visit. Patients who were randomized to placebo during the 6-month treatment period will receive BIVV009; and patients who were randomized to BIVV009 during the 6-month treatment period will receive a placebo dose in order to maintain the blinding. Part B will run for one year following last patient out (LPO) under Part A. In Part B, patients will be dosed with open-label BIVV009 every two weeks, as in Part A. On-site visits will be completed every two weeks when samples for safety and efficacy measures will be collected; samples for pharmacokinetics (PK) and pharmacodynamics (PD) will be collected at visits approximately every three months. Sample for antidrug antibodies will be collected every three months (at a minimum). The study will be complete 12 months following LPO under Part A at which time all patients receiving on-going treatment will proceed to an End-of-Study (EOS) visit 9 weeks after the last administration of study drug.

After Week 39, a subgroup of patients will have their study drug infused at home, every four weeks, alternating with study drug administration during office visits. Additionally, after Week 39, another subgroup of patients will have their study drug administered in the form of infusions undiluted with normal saline.

Study primary analysis will be conducted for Part B after all patients have completed Part B and the data are cleaned.

This statistical analysis plan contains information pertaining to definitions of analysis sets and derived variables, and statistical methods for the analysis of efficacy, safety, PK, and PD for Part B of the referenced study.

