4.1 GENERAL CONSIDERATIONS

Safety, efficacy, and PK/PD data will be summarized using standard summary statistics for continuous, categorical, and time-to-event data. Data will be summarized for the populations defined.

No statistical hypothesis testing is planned.

Continuous Variables

Continuous variables will be summarized using descriptive statistics including the number of non-missing values (n), mean, standard deviation (SD), median, minimum and maximum. Where specified in the table shells, the 25th and 75th percentiles will also be provided. Means, medians, and the 25th and 75th percentiles will be presented to one decimal place beyond that with which the data were captured. SDs will be presented to two decimal places beyond that with which the data were captured. Minimum and maximum will be displayed to the same number of decimal places as that with which the data were captured.

Unless impractical within a given table, statistics will be aligned by the decimal place (or assumed decimal place) in the summary tables.

Categorical Variables

Categorical variables will be summarized by counts and percentages. All percentages will be rounded to one decimal place. The percentage will be suppressed when the count is zero. Unless specified otherwise, the denominator for all percentages will be the number of subjects with non-missing data for a given summarization.

Part B Study Treatment Period

For subjects who enroll into Part B, the Part A study treatment period starts at the date of first study drug administration and ends at the date of Week 26 visit. The Part B study treatment period starts following completion of Part A (ie, immediately following Week 26 visit) and ends at the ET/EOS/Safety follow-up visit, which is 9 weeks after each subject's last dose.

Combined Study Period

The Combined Study Period includes all visits in Part A and Part B and will be utilized for a subset of analyses in order to support regulatory submissions and/or publications.

Thromboembolic Events

Thromboembolic events prior to Part A study entry are recorded as medical history in the eCRFs, while thromboembolic events on Part A and Part B study are captured as adverse events. Both medical history and adverse events will be coded according to Medical Dictionary for Regulatory Activities (MedDRA) v23.0 or higher.

All thromboembolic events reported (as AEs) will be reviewed and determined by internal medical staff via medical adjudication.

Hemolytic Breakthrough

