All AEs within 24 hours after the start of site infusion are captured in the eCRF. Incidence of AEs within 24 hours after the start of site infusion will be summarized by SOC and preferred term.

AEs within 24 Hours after the Start of Home Infusion

All AEs within 24 hours after the start of home infusion are captured in the eCRF. Incidence of AEs within 24 hours after the start of home infusion will be summarized by SOC and preferred term. AEs within 24 hours after the start of home infusion will be flagged on the listing of adverse events.

AEs within 24 Hours after the Start of Undiluted Infusion

All AEs within 24 hours after the start of undiluted infusion are captured in the eCRF. Incidence of AEs within 24 hours after the start of undiluted infusion will be summarized by SOC and preferred term. AEs within 24 hours after the start of undiluted infusion will be flagged in the listing of adverse events.

Infections and Infections of \geq Grade 3 Severity

Infections will be captured based on MedDRA SOC of “infections and infestations.” Incidence of infections of Grade 3 or higher will be summarized by preferred term. Listings of all infections, infections of Grade 3 or higher and serious infections will be provided.

Autoimmune Events

Treatment-emergent autoimmune events will be adjudicated and flagged on the Listing of adverse events.

Hypersensitivity Events

Treatment-emergent hypersensitivity events will be adjudicated and flagged on the Listing of adverse events.

Anti-drug Antibody

Subjects will be evaluated for anti-drug antibodies at Baseline and at the ET/EOS/Safety Follow-up visits in Part B. Subjects with negative or positive anti-drug antibodies at baseline and post baseline, as well as the incidence and prevalence will be summarized for the Combined Study Period by dose cohort in Part B (ie, 6.5 g and 7.5 g) and Total. A listing will be provided for subjects with negative or positive anti-drug antibodies along with the associated titer if available. If applicable, TEAEs for those subjects will be included in the same listing.

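### The Part A SAP evaluates anti-drug antibodies only in early discontinuers and only as a listing, although the protocol samples all patients and promises a positive rate; the Part B SAP only partly fills the gap

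*SAP*

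**What the plan says.** **Protocol.** Section 4.3.8 sets the Part A schedule: "During Part A, ADA samples will be collected at predose on Day 0, 7, 35, 77, 133, 175 and on Day 182 (EOT"), or at early termination. It is not limited to discontinuers. In Part B, samples are taken on Days 189, 217 and 245, then every 3 months from Day 273, and at the follow-up visit 9 weeks after the last dose. The synopsis names pre-existing and treatment-emergent ADA as the outcome measures. Section 3.2 makes immunogenicity an exploratory Part A objective. Section 7.7.1 puts every dosed patient with an evaluable ADA sample in the ADA population, and 7.7.2 leaves the methods to the SAP. Section 7.8.2 adds: "The number and percentage of patients who have positive ADAs will be presented". The opening of Section 7 says the SAP prevails where the two differ.

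**Part A SAP.** The ADA plan in 4.7.2 is two sentences: "Subjects who discontinue treatment early in Part A will be evaluated for anti-drug antibodies" and "Subjects with a positive anti-drug antibody will be listed along with the associated titer, if available". Table 2 has no immunogenicity objective and Table 4 has no ADA set.

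**Part B SAP.** Section 4.7.2 begins: "Subjects will be evaluated for anti-drug antibodies at Baseline and at the ET/EOS/Safety Follow-up visits in Part B". It then plans ADA status at baseline and after baseline, "as well as the incidence and prevalence will be summarized for the Combined Study Period by dose cohort in Part B", with a listing of titers and related adverse events. Section 4.1 defines the period: "The Combined Study Period includes all visits in Part A and Part B". Section 1.1 says: "Sample for antidrug antibodies will be collected every three months (at a minimum").

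**The concern.** The Part A SAP states that it is based on protocol version 6. The amendment history (Appendix J) shows that version 6 added both the immunogenicity objective and the extra ADA time points. The SAP nevertheless narrows evaluation to patients who stop early, and its appendix on changes to planned analyses declares no departure.

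Early discontinuers are a selected subset, and a listing of positives has no denominator. A reader of the Part A report could not say what proportion of BIVV009 patients developed ADA, whether positives were already positive at Day 0, or how BIVV009 compares with placebo. The placebo arm matters because it shows how often the assay turns positive without drug.

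There is also a link to clinical events. Protocol 5.3 names breakthrough attributable to ADA as a ground for withdrawal, and the protocol takes an ADA sample at breakthrough. The breakthrough listing in Part A SAP 4.7.2 shows hemoglobin, bilirubin, LDH and haptoglobin, but not ADA.

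**Working it through.** The documents give no ADA figure to reproduce. The check sets the texts side by side and counts scheduled samples.

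1. **Who is evaluated in Part A.** Protocol 7.7.1: every dosed patient with an evaluable sample. Part A SAP 4.7.2: early discontinuers. These conflict, and the precedence rule resolves the conflict in favor of the SAP.

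2. **What is reported in Part A.** Protocol 7.8.2: number and percentage positive. Part A SAP: a listing. If the listing sentence is read generously as covering all patients, it still gives no denominator, percentage, arm comparison or split by baseline status.

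3. **Samples per Part A completer.** Days 0, 7, 35, 77, 133, 175 and 182 make 7 scheduled samples, 6 of them after baseline. The evaluation sentence assigns none of a completer's 7 to an analysis.

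4. **Samples across the study.** Assume 3 months = 91 days, with Part B dosing of 1 or 2 years as in protocol 4.4.
   - 1 year: Part B has 3 (Days 189, 217, 245) + 4 (Days 273, 364, 455, 546) + 1 follow-up = 8. Total 7 + 8 = 15.
   - 2 years: Part B has 3 + 8 (Days 273 to 910) + 1 = 12. Total 7 + 12 = 19.
   - The Part B evaluation sentence names 2 of these, baseline and the end visit: 2/15 = 13% or 2/19 = 11%. That leaves 13 to 17 unnamed.

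5. **Whether those 13 to 17 are excluded.** Not clearly. The same paragraph summarizes incidence and prevalence over a period that takes in every visit of both parts. Read that way, all samples could count. The paragraph supports both readings.

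6. **Whether Part B replaces the missing Part A table.** Only in part.
   - Its summary is by dose cohort (6.5 g or 7.5 g, set by body weight), so it does not compare BIVV009 with placebo. For former placebo patients, the combined period mixes placebo and active treatment.
   - Part B SAP Section 2 excludes patients who withdrew in Part A. The two plans therefore cover separate groups, and no planned table covers all dosed randomized patients.
   - Part B SAP 4.9 summarizes Part B data only up to the Part A database lock. If the evaluation sentence is taken literally, patients still in Part B at that date would have no end-visit sample and so no post-baseline ADA evaluation in the submission.

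**The case against.** The strongest reply is that the two SAPs complement each other. Early discontinuers are evaluated under the Part A SAP. Patients who roll over get incidence and prevalence over both parts under the Part B SAP. Part B baseline is the last value before the first Part A dose (Part B SAP 5.4), so status at baseline and after baseline is essentially the pre-existing versus treatment-emergent split for those patients. This stands, and it rules out a stronger conclusion that a reader might draw: that the immunogenicity objective cannot be answered at all, or that Part B uses only its first and last samples.

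The breakthrough argument is also narrower than it looks. A patient withdrawn for ADA-related breakthrough is an early discontinuer and is evaluated. Only patients who have a breakthrough and stay on treatment lack a planned link to ADA.

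The protocol promises a number and percentage but does not say by arm, and it leaves methods to the SAP. That is correct. However, Part A SAP 4.7 makes treatment arm the default stratification for safety analyses, so a by-arm table follows the SAP's own convention.

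A reader might also multiply 7 samples by 40 patients and infer that nearly all of 280 samples go unused. The documents do not support this. The first patient was randomized on 16 April 2018, version 6 is dated 15 October 2019, and for patients enrolled before it ADA only may be tested from back-up samples, with consent. The figure 280 is a ceiling, and the Combined Study Period summary may use many of the samples that exist.

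**Conclusion.** The Part A finding holds. The Part A SAP contradicts the protocol on who is evaluated for ADA and on what is reported. Because the SAP prevails, the Part A analysis would give no ADA rate, no arm comparison and no split by baseline status. The Part B finding is one of ambiguity: its text does not settle whether 13 to 17 of 15 to 19 scheduled samples per patient count, given the 91-day assumption and 1 to 2 years of Part B dosing.

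It would be tempting to size the Part A gap with a confidence bound. If 2 or 3 BIVV009 patients stopped early and none was positive, the exact 95% upper limit, 1 − 0.025^(1/n), would be 84% or 71%. This should not be used. The number of discontinuers is not in the documents, the SAP does not propose to estimate incidence from them, and the Part B summary supplies other information.

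Immunogenicity is an exploratory objective in Part A, and no primary or key secondary result depends on it. This should be corrected, but it does not threaten the trial's main conclusions.

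**What to change.** **Part A SAP.** Add an ADA analysis set to Table 4, matching protocol 7.7.1, and the immunogenicity objective to Table 2. Replace the evaluation sentence in 4.7.2 with wording such as: *ADA will be analysed in every dosed patient who has an evaluable ADA sample, using all available samples. The number and percentage with pre-existing and with treatment-emergent ADA will be tabulated by treatment arm, with titer. Positives will be listed together with any hemolytic breakthrough.*

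**Part B SAP.** In 4.7.2, state that all scheduled ADA samples, including Days 189, 217 and 245 and the 3-monthly ones, feed the Combined Study Period incidence and prevalence.

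**Both.** Report how many patients have samples at baseline and after baseline, so that rates are read against what is available for patients enrolled before version 6.

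The cost is SAP wording and one table per part. No sampling is needed beyond what the protocol already schedules. The change is best made before the Part A database lock.

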4.7.3 Additional safety assessments

4.7.3.1 Laboratory variables, vital signs and electrocardiograms (ECGs)

Hematology and Chemistry

All summaries will be structured such that the hematology and chemistry tests are presented in the order shown in the tables below.

Hematology measurements that will be summarized and listed include white blood cell count (WBC), red blood cell count (RBC), differentials (basophils, eosinophils, lymphocytes, monocytes, neutrophils, reticulocytes), hemoglobin, hematocrit, and platelet count.

Chemistry measurements that will be summarized and listed include electrolytes (sodium, potassium, chloride), glucose, total protein, total bilirubin, alanine aminotransferase (ALT), aspartate aminotransferase (AST), alkaline phosphatase (ALP), blood urea nitrogen (BUN), and serum creatinine.

Change from Baseline

Hematology and chemistry results at baseline and post baseline visits, along with change from baseline, will be summarized for the Safety Analysis Set.

Shifts from Baseline

Each subject’s laboratory values will be classified according to whether the test result is “low” (below the LLN), “normal” (within the normal range), or “high” (above the ULN). Shift tables will be constructed based on both the minimum and maximum post-baseline values for each subject. Data collected from unscheduled visits will be included in the determination of the per subject minimum and maximum values. A separate table will be provided which summarizes the results of the shift tables in which the number and percentage of subjects with a shift to low (from normal, high, or unknown) and the number and percentage of subjects with a shift to high (from normal, low, or unknown) will be tabulated; percentages will be based on the number of subjects at risk. The number at risk for a shift to low (high) is the number of subjects who have a baseline value that isn’t low (isn’t high) including unknown, and have at least one post-baseline value. Only directions of change indicating a clinical concern will be included in this table summarizing the shifts. The direction of concern is provided in [Table 10](#).

Table 10 - Direction of change indicating clinical concern for laboratory tests

Laboratory Test	Direction	Laboratory Test	Direction
	Chemistry		Hematology
Liver		White blood cells	Low and High
ALT/SGPT	High	Lymphocytes	Low and High
AST/SGOT	High	Neutrophils	Low and High
Total bilirubin	High	Monocytes	Low and High
GGT	High	Eosinophils	Low and High
Renal		Basophils	Low and High
Blood urea nitrogen	High	Red blood cells	Low and High
Creatinine	High	Hemoglobin	Low and High
Electrolytes		Hematocrit	Low and High
Sodium	Low and High	Platelets	Low and High
Potassium	Low and High		
Chloride	Low and High		
Other			
Glucose	Low and High		
Total protein	Low and High		

Potentially Clinically Significant Laboratory Abnormalities

Abnormal laboratory values (excluding Hgb, reticulocytes, haptoglobin, bilirubin, and LDH) will also be evaluated by determining the number and percentage of subjects with at least one potentially clinically significant laboratory abnormality over the course of the study that also represents a worsening from baseline. The potentially clinically significant levels are based on Grade 2 or higher thresholds from the CTCAE v4.03 where possible or are defined by the Sponsor's safety group. Subjects who have a post baseline laboratory value that meets the criteria for being potentially clinically significant but do not have a baseline value will be included in the numerator for determining the percentage of subjects with an abnormality. Data collected from unscheduled visits will be included in this analysis. The laboratory tests and thresholds for determining PCSAs are provided in [Table 11](#).

Table 11 - Thresholds for potentially clinically significant laboratory abnormalities

T	Threshold	Laboratory Test	Threshold
	Chemistry		Hematology
ALT (U/L)	>= 3 x ULN	Hematocrit (%)	<= 30% >= 60%
Albumin (g/dL)	<= 2.5 g/dL	Hemoglobin (g/L)	<= 100 g/L >= 190 g/L
Alkaline Phosphatase (U/L)	>2.5 x ULN	MCV (fL)	>= 1.2 x ULN <= 0.8 x LLN
AST (U/L)	>= 3 x ULN	Platelet count (10 ⁹ /L)	<= 75 x 10 ⁹ /L >= 700 x 10 ⁹ /L
Blood urea nitrogen (mmol/L)	>= 10.7 mmol/L	WBC (10 ⁹ /L)	<3 x 10 ⁹ /L >= 16 x 10 ⁹ /L
Chloride (mmol/L)	<= 90 mmol/L >= 118 mmol/L	Basophils (10 ⁹ /L)	>1.6 x 10 ⁹ /L
Creatinine (umol/L)	>1.5 x ULN	Eosinophils (10 ⁹ /L)	>1.6 x 10 ⁹ /L
GGT (U/L)	>2.5 x ULN	Lymphocytes (10 ⁹ /L)	>0.8 x 10 ⁹ /L
Glucose (mmol/L)	<3 mmol/L >8.9 mmol/L	Monocytes (10 ⁹ /L)	<2.5 x 10 ⁹ /L
Potassium (mmol/L)	<= 3 mmol/L >= 6 mmol/L	Neutrophils (10 ⁹ /L)	>1.5 x 10 ⁹ /L
Sodium (mmol/L)	<= 126 mmol/L >= 156 mmol/L		
Total bilirubin (umol/L)	>1.5 x ULN		
Direct bilirubin (umol/L)	>1.5 x ULN		
Total protein (g/L)	<= 45 g/L >= 100 g/L		

Systemic Lupus Erythematosus (SLE) Panel

SLE panel will be summarized with descriptive statistics. The number of subjects with all negative or all missing values for all SLE panel parameters prior to receiving study drug and the number of subjects with at least one positive value for at least one SLE panel parameter prior to receiving study drug will be summarized. Further, among subjects who have all negative or all missing values for all SLE parameters prior to receiving study drug and have at least one post-baseline value for at least one parameter, the number of subjects who test negative at all post-baseline assessments for all SLE parameters, and the number of subjects who test positive at any post-baseline assessment for at least one SLE parameter will be summarized.

Similar summaries will be generated for individual SLE parameters. In addition, for a given SLE parameter, among subjects who have at least one positive or all missing values prior to receiving study drug and have at least one post-baseline for this parameter, the number of subjects who test positive at all post-baseline assessments, and the number of subjects who test negative at any post-baseline assessment will be summarized.

Parameters in the SLE Panel are Antinuclear antibody (ANA), multiplex with dsDNA, Anti-La/SSB antibody (SS-B), Anti-ribonucleoprotein antibody (RNP), Anti-Smith antibody (Sm), Anti-Ro/SSA antibody (SS A), Anti-scleroderma antibody (Scl-70), Anti-Chromatin antibody, Anti-Jo-1 antibody, Anti-Centromere B antibody, Circulating immune complexes (CIC).

Disease-Related Biomarkers

Disease-related biomarkers include DAT (polyspecific, anti-IgG & anti-C3d), LDH isoforms, cold agglutinin (CAG) titre, IgG subsets (IgA, IgD, IgG, IgM), vaccine titres, CAG thermal amplitude. Actual values and change from baseline for all biomarkers will be summarized by visit by treatment arm.

Electrocardiogram (ECG)

The proportion of subjects with clinically significant change from baseline in ECG findings will be summarized by visit.

Vital Signs

Vital signs (systolic and diastolic blood pressure, pulse, respiratory rate, and temperature) will be summarized for the observed values and change from baseline using descriptive statistics for the Safety Analysis Set.

The number and percentage of subjects with potentially clinically relevant post-baseline abnormalities will be presented. The criteria for clinically relevant post-baseline abnormalities are shown below in [Table 12](#).

Table 12 - Criteria to determine clinically relevant abnormalities in vital signs

Vital Sign	Criteria for Abnormalities
Temperature	>38°C and an increase from pre-dosing of at least 1°C
Pulse	>120 beats per minute post-baseline, or an increase from pre-dosing of more than 20 beats per minute, or <50 beats per minute post-baseline, or a decrease from pre-dosing of more than 20 beats per minute
Systolic Blood Pressure	>180 mmHg post-baseline, or an increase from pre-dosing of more than 40 mmHg, or <90 mmHg post-baseline, or a decrease from pre-dosing of more than 30 mmHg
Diastolic Blood Pressure	>105 mmHg post-baseline, or an increase from pre-dosing of more than 30 mmHg, or <50 mmHg post-baseline, or a decrease from pre-dosing of more than 20 mmHg
Respiratory Rate	>35 breaths per minute post-baseline, or <10 breaths per minute post-baseline

